8.3.1 Study Treatment

Each Subject will have the treatments described below, during which identical study procedures will be performed during each study treatment.

Treatment 1: Initial standard hemodialysis treatment with heparin (SHH) anticoagulation.

Treatment 2: A single hemodialysis treatment with SCD treatment and regional citrate anticoagulation one week after Treatment 1.

Each subject's safety data will be monitored by the PI on an ongoing basis.

Prior to start of Study Treatment (SHH or SCD Treatment)

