8.4 Detailed Study Measures

8.4.1 Echocardiographic Methods

Complete transthoracic echocardiograms including structural imaging, color Doppler for evaluation of valvular regurgitation, spectral Doppler for hemodynamic quantitation and longitudinal strain in 3 views for calculation of global longitudinal strain (GLS) will be performed at each time point as per the specified protocol.

All echocardiograms will be performed on an identical echocardiographic platform (Epiq, Philips Ultrasound, Andover MA) using identical platform upgrades and software. Standard measures of left ventricular dimensions and volume from which ejection fraction will be calculated will be

performed off-line using the digitized images. The calculation of GLS will be performed using the integrated software of the platform.

Specific echocardiographic parameters to be quantified at each time point are as noted on the echocardiographic case report form.

Because the majority of echocardiographic parameters which reflect left ventricular contractility are both pre-and afterload dependent a substantial range of findings across patients is unavoidable and it is not feasible within the scope of a study this size to identify “normative” values nor is it possible to accurately identify thresholds of change in parameters such as ventricular size or ejection fraction in patients in whom intravascular volume and systemic systolic pressures vary. Each patient will therefore serve as his or her own control comparing pre-and post-dialysis echocardiograms following standard dialysis compared to pre-and post-echocardiograms following investigational dialysis using the SCD device^{36,37}.

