Assessment: Echocardiographic parameters which are less (but not entirely) preload and afterload dependent include quantitation of regional wall motion abnormalities as well as calculation of GLS. Normative values for regional wall motion abnormalities are defined as normal thickening and endocardial excursion in all regions and any deviation from normal thickening or excursion is considered abnormal. Regional wall motion will be scored using a standard wall motion scoring scheme. (1=normal; 2=hypokinetic; 3= akinetic; 4=dyskinetic). Scores will be tabulated for each of 16 predefined segments and a global wall motion score calculated as the sum of individual scores divided by the number visualized segments. For this scheme a score of 1 represents normal ventricular function with progressively higher numbers representing progressively worse systolic function. Scores from pre HD, post HD and 24 hour post HD Echos from all 10 patients will be collated and analyzed for statistical significance between Treatment 1 and Treatment 2 groups.

Global longitudinal strain will be obtained using tissue tracking methodology³⁸. There is a significant range within the left ventricle of normal values for regional strain depending on wall location. Values for normal GLS in normal controls have ranged from -16.0 to -22.0. Patients with systemic diseases including hypertension, diabetes and renal disease have all been described to have reduced GLS in the absence of overt systolic dysfunction. As “normal” values for GLS cannot be predicted in the patient population under consideration each patient will serve as his or her own control for tracking improvement or deterioration in global longitudinal strain.

Assessment: The largest body of data regarding using global longitudinal strain for tracking myocardial performance is in the patients receiving cardiotoxic chemotherapeutic agents where a threshold of 10-15% change has been considered as significant variation from baseline³⁹. This will be used as a dichotomous threshold for defining either improvement or deterioration in GLS.

Echocardiographic images will be interpreted at the Echo Laboratory, Frankel Cardiovascular Center, Floor 3. Area B, University of Michigan, Ann Arbor, MI

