8.5 Study Exit Procedures

A Study Termination form will be completed for all patients who have completed the Study Procedures according to the protocol as well as for those who are terminating early for any cause

9. Statistical Considerations

Sample size determination for primary outcome regional wall abnormalities: Our consultant, [name] has previously demonstrated a difference in this variable in 8 to 10 patients using a similar protocol to this proposal when comparing standard and biofeedback dialysis and dialysis cooling ^{33,34}. Sample size of 10 would appear to be sufficient to detect a difference of 20% and is based upon a standard deviation of 14%, significance level of 0.05 and 80% power. In the [name] studies, differences of greater than 20% were observed. We plan to recruit 10 patients in this study, to better ensure an adequate sample size to obtain statistically relevant primary and secondary endpoint comparisons. The patients will serve as their own controls, comparing BL-SHH parameters to SCD therapy parameters. Independent t-test will be used to compare the peak frequency of MS between SHH and SCD sessions. Global LVEF and wall motion in 16 segments in 8 regions at each time point in the dialysis session will be compared using repeated measures and Bonferroni's test for multiple comparisons. IDWG will be compared using paired and unpaired non-parametric testing or t-test if the variable is

normally distributed. These approaches have shown significance in prior studies for MS in HD. Statistical correlations are planned for regional wall abnormalities, inflammatory indices, monocyte subsets and pre-dialysis blood pressures ^{33,34}

10. Adverse Events

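### The primary wall-motion grade is assigned by a reader, SCD is always the second session, and the plan states no masking or reading order for the echocardiograms

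*Combined protocol and SAP*

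**What the plan says.** - **Outcome.** Section 9 sizes the trial on wall motion: "Sample size determination for primary outcome regional wall abnormalities". Section 8.4.1 adds "Regional wall motion will be scored using a standard wall motion scoring scheme", with grades from 1 (normal) to 4 (dyskinetic), and "Scores will be tabulated for each of 16 predefined segments". The global score is the mean grade over the segments that can be seen.
- **Order.** Section 8.3.1 gives every patient the heparin session first. Treatment 2 is "A single hemodialysis treatment with SCD treatment and regional citrate anticoagulation one week after Treatment 1". Under section 4.1 the device joins the circuit after the first hour, so those running the session know which one it is.
- **Comparison.** "Each patient will therefore serve as his or her own control comparing pre-and post-dialysis echocardiograms", standard session against SCD session (section 8.4.1).
- **Reading.** "Echocardiographic images will be interpreted at the Echo Laboratory". Section 8.4.1 also requires one echo platform and software, and has dimensions and volumes measured off-line from digitized images. It says nothing on masking, reading order, number of readers or reader agreement. It points to an echocardiographic case report form and a specified protocol, neither of which is in the text available.
- **Strain.** "The calculation of GLS will be performed using the integrated software of the platform".
- **Sample size.** "Sample size of 10 would appear to be sufficient to detect a difference of 20" per cent, with a standard deviation of 14%, significance level 0.05 and 80% power. Section 9 names an independent t-test for the comparison of sessions.

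**The concern.** Whether a segment shows stunning turns on whether it is called normal or hypokinetic. The documents do not say that a person makes this call by eye, but it is a fair inference, since images are interpreted at a laboratory and only GLS is assigned to software. Section 3 states the aim as fewer stunning events. A reader who knows that a scan belongs to the SCD session could tilt borderline segments in that direction without intending to.

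Using patients as their own controls removes stable differences between patients. It does not remove an error that changes with the session. Because SCD comes second for everyone, such an error enters each within-patient difference with the same sign. Neither more patients nor a different test would take it out.

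The plan is more careful elsewhere: section 8.4.2 sets assay controls and precision criteria for the soluble markers. The primary outcome has no counterpart.

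**Working it through.** **Inputs.** From section 9: difference 20%, SD 14%, alpha 0.05 (two-sided assumed), power 80%, n = 10 patients with both sessions. From section 8.4.1: 16 segments. Not in the documents: the size of any reader bias, the unit of the 20%, the number of affected segments in the control session, and whether 14% is the SD of values or of within-patient differences.

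**1. The plan's own figure.** Normal approximation for two means: n = 2 × (1.960 + 0.842)² × 14² / 20² = 7.7, so 8 per session. The exact noncentral-t calculation gives 9 per session (power 81.2%), and 10 per session gives 85.5%. The stated 10 is consistent with the independent test. If 14% is the SD of differences, a paired t-test with 10 patients has 97.9% power.

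**2. What one segment is worth.** One segment is 1/16 = 6.25 percentage points of segments. One grade in one segment moves the global score by 1/16 = 0.0625. How this compares with 20% depends on the unit:

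| Reading of 20% | Target | One segment or one grade step is |
|---|---|---|
| Percentage points of 16 segments | 0.20 × 16 = 3.2 segments | 6.25 points |
| Relative to k affected segments (k assumed) | 0.20 × k: 0.6 at k = 3, 1.0 at k = 5, 2.0 at k = 10 | 1/k: 33% at k = 3, 20% at k = 5, 17% at k = 6, 10% at k = 10 |
| Relative to the global score (1.0 to 2.0 assumed) | 0.20 to 0.40, or 3.2 to 6.4 one-grade steps | about 6% to 3% |

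One segment per patient reaches 20% only on the second reading, with k of about 5 or fewer.

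**3. False positives from an assumed bias, percentage-point scale.** The true effect is set to zero and the mean difference equals the bias b. The chance of p < 0.05 follows from the noncentral t distribution:

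- Independent test: noncentrality b / (14 × √(2/10)) = b / 6.26, 18 degrees of freedom. This treats the two sets of ten values as uncorrelated.
- Paired test: noncentrality b / (SD of differences / √10), 9 degrees of freedom. With 14% as the SD of differences this is b / 4.43. The last column uses 14 × √2 = 19.8, which is the case of no within-patient correlation.

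| Average bias (segments) | b (points) | Independent t | Paired t, SD of differences 14 | Paired t, SD of differences 19.8 |
|---|---|---|---|---|
| 0 | 0 | 5% | 5% | 5% |
| 0.5 | 3.125 | 7.6% | 9.7% | 7.3% |
| 1 | 6.25 | 15.7% | 24.4% | 14.6% |
| 2 | 12.5 | 47.2% | 71.0% | 43.0% |
| 3.2 | 20 | 85.5% | 97.9% | 81.1% |

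**4. Smallest significant difference.** Independent: 2.101 × 14 × √(2/10) = 13.2 points, and 0.132 × 16 = 2.1 segments. Paired: 2.262 × 14 / √10 = 10.0 points, and 0.100 × 16 = 1.6 segments. Both are well below the 3.2-segment target.

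**The case against.** - **It is an exploratory pilot.** Section 4.1 says so, and the synopsis calls the primary analyses descriptive. This lowers the stakes. But section 9 powers this outcome and names a test for it, and section 8.4.1 plans a significance comparison between treatments, so a p-value will be produced and read.
- **Other measures are less exposed.** GLS comes from platform software on an identical system in three views, and the soluble markers and flow cytometry are laboratory results. Agreement among them would be partial corroboration. They do not protect the primary score, and no masking is stated for GLS either. The documents describe no discretionary choice of view or tracking, so a bias in GLS would be speculation.
- **The reader may not know the session.** The Echo Laboratory is named separately from the dialysis unit, and the post-session echo is listed after the circuit is taken apart. The scan date reveals the treatment only to someone who knows the sequence. The plan does not say what the reader is told. Masking might also be set out in the case report form or echo protocol that 8.4.1 cites; if so, a cross-reference would settle the point.
- **The size is unknown.** This stands. A reader might infer that expectation alone can create a difference as large as the one the trial seeks. The documents do not support that as a general statement: they give no bias figure, and on the percentage-point scale it would take an average shift of 3.2 segments per patient. A reader might also infer that a positive result could never be told apart from expectation. That ignores the corroboration from GLS and the laboratory markers.

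**Conclusion.** The point holds as a gap in bias control for the primary outcome. In the available text, a reader-assigned grade is compared between sessions in a fixed order, with no masking of session or time point and no reading order. Any expectation bias would be aligned with treatment and would survive the pairing.

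Its size can be stated only conditionally. On the percentage-point scale, with SD 14%, 10 patients and no true effect, an assumed average bias of one segment takes the false-positive rate from 5% to about 16% (independent t) or 24% (paired t, 14% as the SD of differences). Nominal significance needs an observed difference of only 2.1 or 1.6 segments. Whether one segment is comparable to the planned effect cannot be settled, because section 9 does not give the unit of its 20%. This is a cheap improvement; confidence is medium, since the bias is assumed and the cited echo documents were not available.

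**What to change.** Amend section 8.4.1 so that:

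- wall motion, and GLS where stored loops allow, is scored by the Echo Laboratory from clips stripped of identity, date, session and time point;
- each patient's six scans (before, after and at 24 hours, for both sessions) are read in computer-generated random order after the last scan;
- scores are locked before unmasking;
- any unmasked clinical look at a scan is done by existing laboratory staff other than the person scoring, and does not feed the endpoint.

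If the cited echo protocol already provides this, a cross-reference is enough.

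**Cost.** Protocol wording, file de-identification and a reading delay: the last scan falls about 7 + 1 = 8 days after the first session. No extra scan or patient is needed, the sample size does not change, and existing staff can do the reading.

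**Limits.** Scans before and after dialysis may remain partly recognisable; heparin against SCD, the comparison that matters, is the one that can be masked. Masking the reader does not remove period effects from the fixed order, nor any influence of unmasked image acquisition.

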8.4.2 Soluble Markers Assay Methods

Assays for soluble markers (Table 3) are either sandwich or competitive ELISAs' and will be performed according to manufacturer's suggested protocols. High sensitivity Quantikine kits from R&D Systems will be run with Quantikine® Immunoassay Control Group 10 Catalog Number: QC41 which provides high, medium and low reference for high sensitivity kits, including IL-1 β , IL-6, IL-8, IL-10 and TNF α . MCP-1 Quantikine kit will be run with Immunoassay Control Group 1 Catalog Number: QC01-1, which provides high, medium and low reference for a wide range of soluble markers including MCP-1. Inter assay controls are provided within the kits for CD62L, elastase, hsCRP, and neopterin. The 96 well format plates will be read using a Molecular Devices Spectramax M5 plate reader, and acquired data analyzed using SoftMax Pro 6.5.1 Software. Inter and Intra Assay precision will be calculated and criteria for acceptance established using expected values provided by the kit manufacturers. Non-compliant analysis will be repeated until criteria are met.

The slated soluble markers are expected to deviate from reported normal values with in patient populations with myocardial stunning. Baseline values will be compared to reported normal and diseased values as reported in the literature and where reported by kit manufacturers. Each patient's pre-treatment value will be used as its own baseline and this value compared to those obtained with the normal hemodialysis session and with SCD therapy. Statistical significance of assay values will be determined using Anova for repeated measures and paired student t test where appropriate.

Table 3. Assays for Soluble Markers

Soluble Marker	Assay Kit	Assay Type	Inter Assay Controls
Elastase	ThermoFisher BMS269	Sandwich ELISA	High/Low Included in Kit
Hs CRP	ALPCO 30-9710s	Sandwich ELISA	High/Low Included in Kit
IL-1 β	R&D Systems HSLB00D	Sandwich ELISA	R&D Systems QC41
IL-6	R&D Systems HS600B	Sandwich ELISA	R&D Systems QC41
IL-8	R&D Systems HS800	Sandwich ELISA	R&D Systems QC41

IL-10	R&D Systems HS100C	Sandwich ELISA	R&D Systems QC41
TNF α	R&D Systems HSTA00E	Sandwich ELISA	R&D Systems QC41
CD62L (L-Selectin)	Abcam	Sandwich ELISA	Single Control
MCP-1	R&D systems DCP00	Sandwich ELISA	R&D Systems QC01-1
Neopterin	TECAN IBL RE59321	Competitive ELISA	High/Low Included in Kit

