Treatment Plan	Each Subject will receive one standard study hemodialysis treatment with heparin anticoagulation during which all procedures noted in Appendix 1 will be performed. Subsequently each subject will receive hemodialysis with the added SCD filter anticoagulated with regional citrate.
Data Safety Monitoring	This is a small feasibility study. A safety analysis will be performed on each patient prior to their next hemodialysis treatment by the PI.
Key Measurements	
 ❖ Adverse events ❖ Regional wall abnormalities and myocardial strain on Echocardiogram
Exploratory Measurements	
 ❖ Soluble Markers (Elastase, Hs CRP, IL-6, IL-10, IL-17, IL-23, G-CSF, TNF-α, MCP-1, L-selectin, neopterin, IL-1β, IL-8) ❖ Leukocyte flow cytometry (circulatory monocyte subsets and circulatory activated neutrophils) ❖ WBC and platelet counts

Primary Analyses	Descriptive analysis will be conducted on the following parameters in all Subjects exposed to any study hemodialysis treatment: 
 ❖ Adverse events ❖ Regional wall abnormalities and myocardial strain ❖ Clinical laboratory and physiological measurements
Secondary Analyses	A number of secondary analyses will be conducted, including the following: 
 ❖ Mean change from baseline in cytokines at the end of each treatment ❖ Mean change from baseline in markers of inflammation at the end each treatment
Study Periods and Study Duration	
 ❖ The total duration of participation will be approximately 3 weeks.

1. Background and Rationale

More than 400,000 people are currently treated by hemodialysis (HD) in the US end stage renal disease (ESRD) program. The mortality in this group of patients is unacceptably high with almost half of the deaths due to cardiovascular disease (CVD). Strategies to reduce the mortality of HD patients with directed interventions at cardiovascular risk factors have largely been ineffective. It is well recognized that HD patients suffer excess morbidity and mortality, mainly due to cardiac failure and sudden death rather than traditional thrombotic occlusion leading to acute myocardial infarction (AMI).^{1,2} The excess cardiovascular risk is not the result of the traditional factors associated with CVD but a combination of non-traditional factors unique to chronic kidney disease (CKD).

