8.12 Exploratory Measurements

- ❖ Soluble Markers (Elastase, Hs CRP, IL-6, IL-10, TNF- α , L-Selectin, MCP-1, IL-17, IL-23, IL-8, G-CSF, IL-1 β , WBC, platelet count, Neopterin)
- ❖ Leukocyte flow cytometry (circulatory monocyte subsets)
- ❖ SCD integrity monitoring during treatment will include visual inspection for clotting and hemolysis, and additional testing following return of hemofilter to the research laboratory.

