8.4.3 Flow Cytometry Methods

Blood will be drawn into EDTA tubes and processed immediately on wet ice. Erythrocytes will be lysed with ammonium chloride buffer, and remaining leukocytes washed by centrifugation and suspended in protein free buffer for live dead labelling to allow for the elimination of false positives. Leukocytes will be transferred at 106 cells/100 μ L/test into tubes containing the following antibody cocktails and incubated for 30 minutes. Tubes will be simultaneously fixed and undergo secondary lysis with BD FACS lyse buffer which has the added benefit of allowing leukocyte cell populations to be identified using scatter profiles.

In Panel 1, antibodies targeting human CD91, CD14, CD16, HLADR, CD192 and CD197 will be used to determine changes in the circulating monocyte population. Neutrophils and monocytes mobilize intracellular stores of CD11b to the cell surface as they become activated, allowing a real-time measurement of systemic acute neutrophil and monocyte activation. Blood treated with a saturating amount of anti-human CD11b allowing for the quantitative analysis of expression to be reported as relative fluorescence intensity.

Systemic Blood Panel 1: CD11b acute activation and MO subtypes

Target	Channel	Vendor	Catalog#	Clone
CD11b	BL1-FITC	BioRAD	MCA551F	ICRF44
CD91	BL2-PE	ThermoFisher	12-0919-42	A2MR-a2
CD14	BL3-PerCP Cy5.5	BioRAD	MCA1568	Tük4
CD192	RL1-Alexa Fluor 647	BD Biosciences	558406	48607
CD16	RL3-APC H7	BD Biosciences	560195	3G8
CD197	VL1-BV421	BioLegend	353208	Go43H7
Live Dead	VL2-Fixable Aqua	ThermoFisher	L34966	NA
HLA-DR	V3-BV605,	BD Biosciences	562845	TU36

Using panel 2, platelet activation will be measured by the percentage of platelets associated with monocyte using the pan monocyte marker CD91 and the platelet membrane glycoprotein recognized by anti-human CD42a. Neutrophil life cycle will be evaluated using anti-human CD10, CD184 (CXCR4) and CD177. Immature neutrophils do not express CD10, while

CD177 and CD184 are expressed on aging neutrophils. A saturating amount of CD62L (L-selectin) will be used to allow for comparison of this activation marker across neutrophil subsets.

Systemic Blood Panel 2: CD62 on NE, monocyte platelet aggregates

Target	Channel	Vendor	Catalog#	Clone
CD62L	BL1-FITC	BD Biosciences	555543	DREG-56
CD91	BL2-PE	ThermoFisher	12-0919-42	A2MR-a2
CD10	BL3-PERCP Cy5.5	BD Biosciences	563508	HI10a
CD42a	RL1-Alexa Fluor 647	BioRAD	MCA1227A647	GRP-P

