Appendix 1. Schedule of Events

Event	4-week Screening Period	Hemodialysis (Procedures to be repeated on days study hemodialysis treatment(s) are given)							24 hour after (± 4 hours)
		Pre-Rx Baseline (time 0)	Rx start >0-<1h	1h	2h	3h	4h	5h	
Informed consent	X								
Review of entry criteria	X								
Echocardiogram ¹		X							X X
albumin		X							
Basic Metabolic Panel ⁶		X							X
CBC/diff/plt ⁶		X							X X
Pregnancy test ⁴	X								
Systemic soluble markers ²		X							X X
Leukocyte flow cytometry		X							X X
Physical examination		X							
Review/update medical history		X							
BP, HR, RR ⁵		X	X	X	X	X	X	X	X
Weight/temp		X							X
Concomitant medications	X	X	X	X	X	X	X	X	x
Adverse events		X	X	X	X	X	X	X	x
iCa ^{3,6}				X ⁷	X	X	X	X	
Visual inspection for hemolysis and clotting in blood circuit							X		

Notes:

1. Hemodialysis procedures should begin within 2 hours of completion of echocardiogram and completion of baseline procedures (physical examination, review/update medical history, vital signs (BP, HR, RR Weight/temp) and recording and review of concomitant medications.
2. Elastase, Hs CRP, IL-6, IL-10, IL-17, IL-23, G-CSF, TNF- α , MCP-1, IL-17, IL-23, IL-8, G-CSF, IL-1 β , Neopterin.
3. For SCD Treatment Protocol only, iCa will be drawn. Levels of iCa will be determined from extracorporeal circuit before citrate infusion site. Additional iCa may be obtained if clinically indicated and post SCD treatment session, upon PI's determination.
4. Pregnancy test: Quantitative bHCG test will be obtained in the screening period.
5. Vital signs (BP, HR, RR) would be recorded within 20 minutes of indicated times.
6. iCa, CBC/diff=plt, basic metabolic panel would be collected within 15 minutes of indicated times.
7. For SCD Treatment Protocol only, iCa will be drawn during this hour just prior to initiation of therapy, and within 10 minutes of starting therapy.

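### The soluble-marker lists contradict each other, and marker and flow results are to be tested for significance with no stated level, lead readout, time point or multiplicity rule

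*Combined protocol and SAP*

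**What the plan says.** - **Synopsis, Exploratory Measurements:** 13 soluble markers, beginning "Soluble Markers (Elastase, Hs CRP, IL-6, IL-10, IL-17, IL-23, G-CSF". Under Secondary Analyses, the same synopsis lists mean changes in cytokines and in inflammation markers to the end of each treatment.
- **Section 8.12:** the same 13, including "MCP-1, IL-17, IL-23, IL-8, G-CSF", with WBC and platelet count placed in the same line.
- **Section 8.4.2:** "Assays for soluble markers (Table 3) are either sandwich or competitive ELISAs". Table 3 has ten rows. The text on assay controls names the same ten analytes and ends with "Inter assay controls are provided within the kits for CD62L, elastase, hsCRP, and neopterin".
- **Appendix 1, note 2:** IL-17, IL-23 and G-CSF are named once and then again in "IL-17, IL-23, IL-8, G-CSF". L-selectin does not appear.
- **Sections 8.4.2 and 8.4.3:** statistical significance is to be judged by repeated-measures ANOVA and paired t tests as appropriate. In 8.4.3 this applies to cell percentages and fluorescence intensities, whose number is not given.
- **Section 9:** a 0.05 level appears only in the sample-size sentence for regional wall abnormalities. Bonferroni is named only for LVEF and wall motion. Ten patients are recruited partly "to obtain statistically relevant primary and secondary endpoint comparisons".

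**The concern.** There are two linked problems.

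First, staff who follow the protocol cannot tell which markers are outcomes. Under Table 3, three listed markers that feed a stated secondary analysis are never produced. Under the Appendix 1 footnote, one marker that has an assay is not on the list.

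Second, the set of tests is open. The plan does not fix which markers count, which comparison is made, at which time, or at what level. With 10 patients and many readouts, some nominally significant differences between the sessions can be expected by chance. A reader of the report could not tell these from a device effect, nor see whether markers were added or dropped after the data were known.

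**Working it through.** **The plan's own figure.** The plan gives no error rate for the markers. Its only computed figure is the sample size of 10 for wall abnormalities. That reproduces: a difference of 20 and an SD of 14, taken as a paired t test with SD of the difference 14 × √2 = 19.8, needs 10 patients (81% power at n = 10). It says nothing about markers.

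**Step 1: the lists side by side.**

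| Marker | Synopsis | 8.12 | Table 3 | Appendix 1 note 2 |
|---|---|---|---|---|
| Nine markers common to all lists | yes | yes | yes | yes |
| L-selectin | yes | yes | yes | **no** |
| IL-17, IL-23, G-CSF | yes | yes | **no** | yes, each twice |
| Distinct soluble markers | 13 | 13 | 10 | 12 |

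Appendix 1 note 2 has 15 entries; less 3 repeats, that leaves 12. A row lost when the PDF was read does not explain Table 3, because the control text in 8.4.2 independently names exactly its ten analytes (five on one control set, MCP-1 on another, four with in-kit controls: 5 + 1 + 4 = 10).

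**Step 2: how many tests.** Soluble markers are drawn before treatment, at 5 h and at 24 h (section 8.3.1, Appendix 1). Appendix 2 agrees: 66 mL / 11 mL = 6 draws = 3 times × 2 sessions. Comparing the two sessions gives:
- one test per marker: 10 to 13 tests;
- one test per marker at each of 5 h and 24 h: 20 to 26 tests.

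**Step 3: chance of at least one false positive.** Assume 0.05 two-sided per test, no true effects and independent tests. The chance is 1 − 0.95^k and the expected number is 0.05k. For the direction that favours SCD, the chance is 1 − 0.975^k.

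| Tests k | At least one, either direction | Expected number | At least one favouring SCD |
|---|---|---|---|
| 10 | 40% | 0.50 | 22% |
| 13 | 49% | 0.65 | 28% |
| 20 | 64% | 1.00 | 40% |
| 26 | 74% | 1.30 | 48% |

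**Step 4: correlation.** Inflammatory markers are likely to move together. Simulating 20,000 trials of 10 patients, with paired t tests and equal correlation between readouts (assumed values), gives for either direction:

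| Tests k | Correlation 0.3 | 0.5 | 0.7 |
|---|---|---|---|
| 10 | 36% | 30% | 23% |
| 13 | 43% | 36% | 27% |
| 26 | 64% | 51% | 36% |

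**Step 5: price of full adjustment.** Bonferroni over 10 or 13 markers means 0.005 or 0.0038 per test. With 10 pairs and 80% power, the detectable standardised paired difference is then about 1.48 or 1.54. At an unadjusted 0.05 it is about 1.0 (20/19.8 = 1.01, from the sample-size check above). This argues for a short lead list rather than adjustment across everything.

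**The case against.** The strongest reply is that these are exploratory measurements. The synopsis and 8.12 head them so, and section 4.1 calls the trial an exploratory pilot. Unadjusted p-values are common in that setting and do no harm if read as descriptive. Repeated-measures ANOVA can also give one overall test per marker, and the synopsis secondary analyses refer to one time only, the end of treatment. On that reading the count is 10 to 13, not 20 to 26. Benjamini-Hochberg is one option among several.

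Much of this stands. It lowers the size of the problem and makes any particular adjustment method a matter of choice. It does not remove the point: the same markers are also secondary analyses, section 9 wants statistical comparisons of secondary endpoints, and nothing says that the p-values are descriptive.

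On the lists, the L-selectin omission sits in one footnote that also repeats three markers, so it looks like a copying slip. Appendix 2 has one common draw for all soluble markers, so no sample is lost. That is fair for L-selectin. It does not explain the three markers without an assay.

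A reader might also take section 8.4.3 ("Neutrophil life cycle will be evaluated using anti-human CD10, CD184 (CXCR4) and CD177") as a further mismatch, because CD184 is not in the Panel 2 table as extracted. That table is broken in the extracted text and a row may have been lost, so no defect can be claimed.

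**Conclusion.** The list conflict is exact and needs no assumption: 13, 10 and 12 distinct markers, three without an assay and one missing from the schedule's list. The lack of multiplicity control for markers and flow is also plain from the text.

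The size of the second problem is conditional. It rests on 0.05 per test (stated only for the primary sample size), two-sided tests, no true effects and independence. On those terms, at least one chance positive has a probability of 40-49% for the soluble markers with one test each, and 64-74% if both post-baseline samples are tested. Assumed correlations of 0.3 to 0.7 bring the 26-test figure down from 74% to between 64% and 36%. About half of the false positives would favour SCD.

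Three stronger readings are not supported:
- A reader might infer that a chance positive is near certain. A probability of 90% needs about 45 independent tests (1 − 0.95^45 = 0.90). That requires a number of flow readouts the plan never gives, tests at both times, and no correlation.
- A reader might infer that the case for the device's mechanism depends on these results. Section 1 bases the mechanism on earlier studies, and section 3 sets myocardial stunning as the objective.
- A reader might assume that missing markers could be measured later from stored plasma. The documents describe no plasma bank.

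The change should be made, but the point does not threaten the primary comparison.

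**What to change.** 1. Use one marker list in the synopsis, 8.12, Table 3 and Appendix 1 note 2. Either add assays and controls for IL-17, IL-23 and G-CSF to 8.4.2 or delete the three everywhere. Restore L-selectin to note 2 and remove the repeats.
2. Before results are seen, name two or three lead marker or flow readouts and the comparison between sessions, at the end-of-treatment time that the synopsis already uses.
3. State the significance level and the multiplicity rule (for example Benjamini-Hochberg), and reserve the word *significant* for results that pass it.
4. Report all other marker and flow results, including the 24 h values, as estimates with confidence intervals, and label any p-values descriptive.

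The cost is wording, plus extra kits if the three markers are kept. The downside is that fewer markers will be called significant; the short lead list limits the loss of power.
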